Subdomain	Test name and Task description
Executive function and attention	Indicate direction of central arrow when flanking arrows are pointing in the same or opposite direction. (6 minutes)
Executive function category switching	Alternate sorting according to shape or color. (7 minutes)
Working memory	Repeat the order of items (2-8) according to size in 1 category then repeat the order of items according to size in 2 categories of items. (7 minutes)
Processing speed	Identify items images (side by side) as "same" or "not the same". (2 minutes)
Episodic memory	Place pictures of individuals performing different tasks in the order they are shown. (9 minutes)
Written word pronunciation	Read printed words aloud. (6 minutes)
Auditory and word-visual picture matching	Match a single word to one of four pictures. (4 minutes)

Table 2: NIH Toolbox Cognition Battery Tests

- **Curcumin Levels:** These will be measured to evaluate the bioavailability of curcumin and its metabolites in CKD. The measurements will be conducted by [name] on a fee-for-service basis in the iC42 Laboratory in the UC-Denver Anschutz Medical Campus according to the method described by Cao *et al.* ³⁸. Curcumin (Acros Organics, Morris Plains, NJ), curcumin *O*-glucuronide and curcumin *O*-sulfate (Cell Mosaic, Worcester, MA), demethoxycurcumin and bisdemethoxy-curcumin (Sigma Aldrich), and tetrahydrocurcumin (ChromaDex, Irvine, CA) will be used in to perform liquid chromatography utilizing high-end mass spectrometry systems. The internal standard (IS) hesperetin will be purchased from 4C Pharma Scientific Inc. (ON, Canada). Heparin-treated human plasma, collected from the study participants and stored at -80 °C, will be used.

- **Clinical labs:** These include basic metabolic profile (and estimated GFR), cystatin C, ACR, Hemoglobin A_{1C}, and lipid profile will be measured by the UIHC clinical lab.

REFERENCES

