STATISTICAL ANALYSIS PLAN

NCT03223883

August 19, 2024

Statistical considerations and power calculation

BA-FMD is the primary outcome of this randomized controlled trial. The change in BA-FMD from baseline to 12 months after randomization will be compared between the curcumin and placebo groups. Other secondary outcomes include aPWV, systemic and endothelial markers of inflammation and oxidative stress, and cognitive function measured by the NIH Cognition Toolbox Battery. Power and sample size calculation ¹⁻³ is based on two-sample t-test of change in FMD by using PASS⁴. Preliminary data provides estimate of the mean and standard deviation (SD) of BA-FMD change as 1.25 and 0.88 under curcumin (n=17) and 0.08 and 0.40 under placebo (n=13), respectively. This provides a large between-conditions difference (i.e. 1.25 - 0.08 = 1.13) and effect of 1.7 taking account heterogeneity. Given the sample mean of 0.08 under control condition of usual care in Van Craenenbroeck, et al.⁵, we have assumed 0.10 as mean change in BA-FMD under placebo conditions. While there is no published literature to estimate the mean change in BA-FMD under curcumin in CKD, we believe it should be smaller than 1.25; in other words, the between conditions difference should be smaller than 1.13. Based on Van Craenenbroeck, et al. ⁵ and Thambyrajah, et al. ⁶ where the betweenconditions difference was 0.33 and 0.80, respectively, we assumed a difference of 0.6 between curcumin and placebo, considering difference between studies in intervention, study population, duration of study, and the observed difference in preliminary data. In summary we have the following assumptions: mean and SD of FMD change from baseline to 12 months after randomization are 0.70 and 0.90 under curcumin and 0.10 and 0.40 under placebo, respectively. With target power of 95% and 2-sided alpha 0.05, calculation by PASS indicates a sample size of 37 patients per group. We are going to enroll a total of 88 patients assuming approximately 18% potential loss to follow-up and equal randomization to the curcumin and placebo groups with 44 participants in each group. Power for cognitive function and other secondary outcomes: Based on the preliminary data from our pilot study of 12 weeks treatment (curcumin vs. placebo) with small sample size (17 patients per group), improved cognitive function was observed in the curcumin group but not in placebo. The effect size for episodic memory can be estimated as 0.8 for both picture sequence memory (data showed 0.77) and fluid composite (data showed 0.83). This implies that 37 patients per group will provide more than 90% power, based on calculation by PASS, with 2-sided significant level of 0.05 by using the two-sample t-test. Similarly, for other secondary outcomes, including change in aPWV and systemic and endothelial markers of inflammation and oxidative stress, 37 patients per group will provide more than 90% power if the effect size is 0.8 or larger. The power will be at least 95% if 44 patients per group can be included and effect size is 0.8.

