
Statistical analysis

Descriptive statistics will be provided for demographic characteristics, baseline measure, and outcome variables as appropriate. For example, mean and SD will be provided for continuous variables and proportion for categorical variables. 95% confidence intervals will also be provided if appropriate. We don't anticipate necessary data transformation but will confirm it before analysis.

All outcome analyses will be based on the "intent-to-treat (ITT)" principle. For Aim 1a, change in BA-FMD from baseline to 12 months after randomization will be compared between curcumin and placebo groups by using two-sample t-test. The same analysis will be performed for aPWV. As an additiaonI analysis, repeated measures analysis will be employed to compare the two groups in the change in both BA-FMD and aPWV from baseline to month 6 and 12, and the compound symmetry covariance structure will be specified. Treatment group indicator, time, and their interaction will be included as fixed effects in the model. We will explore the impact of sex, race, baseline CKD stage, and physical activity by including them as covariates in a regression model. Of note, we are stratifying by age and DM status (as noted above). For Aim 1b, repeated measures analysis will be performed for change in both BA-FMD and aPWV before and after vitamin C infusion at all three time points, the same analysis as the previous one in Aim 1a except that we now have three time points and that other covariance structures will also be explored. In addition, correlation analysis will be performed to examine the association between change in vascular function (BA-FMD and aPWV) and change in levels of inflammatory and oxidant markers including systemic measures (high-sensitivity CRP, IL-6, MCP-1, and oxLDL) and endothelial measures (eNOS and eNOS phosphorylated at Ser 1177, NF-κB, NAD(P)H oxidase,

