and nitrotyrosine). Finally, repeated measures analysis will be employed to compare between groups the change in inflammatory and oxidant markers from baseline to month 6 and 12. For Aim 2, the same analysis as in Aim 1a will be performed to evaluate the treatment efficacy on cognitive function, including correlation analysis to examine the association between change in vascular function (BA-FMD and aPWV) and cognitive function. Based on our pilot study, we don't anticipate severe adverse events but we will tabulate all observed events. Data of pill count will be summarized and analyzed as appropriate. All analyses will be performed by using SAS 9.4, SAS Institute Inc., Cary, NC, USA⁷.

Loss to follow-up and missing data: We anticipate loss to follow-up and missing values will occur, but based on our experience and track record we do not anticipate large number of loss to follow-up. We thus plan to derive conclusions based on complete case analysis by using two-sample t-test of the outcome variables. We will tabulate baseline characteristics to examine any difference between those lost to follow up and those complete the study. In the unlikely event of >10% missing data, we will perform multiple imputation under assumption of missing at random (MAR) mechanism ⁸ and examine any change in conclusions.

References

1. Julious SA. Sample Sizes for Clinical Trials. Second Edition ed. Boca Raton, FL: Chapman and Hall/CRC; 2010.

3. Zar JH. Biostatistical analysis. Second Edition ed. Englewood Cliffs, New Jersey: Prentice- Hall; 1984.

4. PASS 14 Power Analysis and Sample Size Software. NCSS, LLC., 2015. at ncss.com/software/pass.)

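### The Aim 2 t-test of change is valid but leaves the collected baseline cognitive score unadjusted; secondarily, the SAP does not say which of two powered scores answers Aim 2

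*SAP*

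**What the plan says.** The SAP lists "cognitive function measured by the NIH Cognition Toolbox Battery" among the secondary outcomes; BA-FMD is primary. The whole Aim 2 efficacy analysis is one clause: "For Aim 2, the same analysis as in Aim 1a will be performed to evaluate the treatment efficacy on cognitive function". The main Aim 1a analysis it points to is that "change in BA-FMD from baseline to 12 months after randomization will be compared between curcumin and placebo groups by using two-sample t-test". The missing-data paragraph confirms that this is the test that counts: "We thus plan to derive conclusions based on complete case analysis by using two-sample t-test of the outcome variables".

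Aim 1a has two further analyses. The repeated measures model contains group, time and their interaction. The exploratory regression adds sex, race, CKD stage at entry and physical activity. The baseline value of the outcome is a covariate in neither.

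The protocol (Experimental Design; Sessions 2 and 7) has the cognitive battery given at baseline and at month 12, with no month-6 assessment.

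On power, the SAP says that the "effect size for episodic memory can be estimated as 0.8 for both picture sequence memory (data showed 0.77) and fluid composite" (0.83 in the pilot for the composite). It continues: "This implies that 37 patients per group will provide more than 90% power", "with 2-sided significant level of 0.05 by using the two-sample t-test". No sentence in either document says which of these two scores answers Aim 2, or how they are to be combined or ordered.

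**The concern.** Two features of the Aim 2 text stand out.

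**Baseline adjustment.** A person's cognitive score at entry is likely to predict the score a year later. Subtracting the baseline uses that information with a fixed slope of 1. ANCOVA estimates the slope instead. When the true slope is below 1, the change score carries baseline noise that could have been removed. The repeated measures analysis does not recover it. With only two cognitive time points and complete data, its group-by-time contrast is the same comparison of mean change.

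**Deciding score.** Aim 1a tests one named variable for each conclusion. Aim 2 inherits the test but names no score, while the power text treats two scores at the full 0.05.

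At stake are the precision of the cognitive comparison and the clarity of the Aim 2 conclusion. Cognition is a specific aim and one of the protocol's two reasons for a 12-month study, so the answer should be as sharp and as unambiguous as the existing data allow.

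**Working it through.** **Inputs from the SAP:** 37 evaluable and 44 enrolled per group; two-sided 0.05; two-sample t-test; effect size 0.8 (pilot 0.77 and 0.83). I take the effect size as the difference in mean change divided by the SD of change.

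**Assumed, not in the documents:** equal SD at baseline and month 12; baseline to month-12 correlation r of 0.5 to 0.9; for the second part, the make-up of the composite and the between-test correlations.

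**1. The plan's own figure.** The power is from the noncentral t distribution with 2n − 2 degrees of freedom and noncentrality d√(n/2). For n = 37 and d = 0.8 the noncentrality is 0.8 × √18.5 = 3.44.

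| n per group | d | Power at 0.05 |
|---|---|---|
| 37 | 0.77 | 90.4% |
| 37 | 0.80 | 92.4% |
| 37 | 0.83 | 94.1% |
| 44 | 0.80 | 96.0% |

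The stated figures (more than 90% with 37, at least 95% with 44) reproduce for one score tested at 0.05.

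**2. ANCOVA against change score.** Let σ0 and σ1 be the SDs at baseline and month 12.

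- Variance of change: σ0² + σ1² − 2rσ0σ1.
- Residual variance under ANCOVA: σ1²(1 − r²).
- Difference: (σ0 − rσ1)², which is never negative.

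So, apart from one degree of freedom, ANCOVA cannot be less precise, whatever the variances. With σ0 = σ1 the ratio is (1 − r²) / [2(1 − r)] = (1 + r)/2, and the effect size becomes 0.8/√ratio.

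| r | Variance ratio | Reduction | Effective d | Power, n = 37 | t-test n per group for the same precision |
|---|---|---|---|---|---|
| 0.5 | 0.75 | 25% | 0.924 | 97.5% | 37/0.75 = 49.3 |
| 0.7 | 0.85 | 15% | 0.868 | 95.7% | 37/0.85 = 43.5 |
| 0.9 | 0.95 | 5% | 0.821 | 93.6% | 37/0.95 = 38.9 |

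The comparison is 92.4% for the unadjusted test. At an illustrative smaller effect of 0.6, which is not in the cognition power text, 72.1% becomes 83.6% (r = 0.5) to 74.3% (r = 0.9).

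**3. Two scores at 0.05 each.** Suppose that significance on either score could carry Aim 2. Take the composite as the average of k equally correlated tests (correlation ρ), one of them picture sequence memory. Its correlation with that test is c = √[(1 + (k − 1)ρ)/k]. The chance of at least one false significant result then follows from the bivariate normal distribution:

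| k | ρ | c | Either direction | Favouring curcumin |
|---|---|---|---|---|
| 5 | 0 | 0.447 | 9.2% | 4.6% |
| 5 | 0.5 | 0.775 | 8.0% | 4.0% |
| 5 | 0.7 | 0.872 | 7.3% | 3.6% |
| 7 | 0 | 0.378 | 9.4% | 4.7% |
| 7 | 0.7 | 0.862 | 7.4% | 3.7% |

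The nominal values are 5% and 2.5%.

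**4. Two ways of closing the choice.** Naming one score at 0.05 keeps 92.4% (n = 37) and 96.0% (n = 44). Keeping both at 0.025 each gives 87.3% and 92.7% at effect 0.8, below the stated 90% and 95%.

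**The case against.** The strongest reply is that nothing is broken. The change-score test is unbiased under randomisation, already uses the baseline by subtraction, and delivers the power the SAP claims. The gain from ANCOVA depends on a correlation and on variances that the documents do not give; at r = 0.9 it is 1.2 percentage points. The same test is used for BA-FMD and aPWV, so the point is not peculiar to cognition. All of this stands. It limits the size of the gain but not its direction, and it is a reason to apply the same change to the Aim 1a outcomes.

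On the deciding score, cognition is secondary, neither document promises error control across secondary outcomes, and neither says that a result on either score will be claimed as efficacy. This also stands: the 7% to 9% is conditional on that reading and on an assumed composite. What remains is an unwritten rule.

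Stronger readings are tempting but unsupported:

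- A reader might infer that the t-test is biased or that the power statement is wrong. Neither follows; the stated power reproduces.
- A reader might infer that any test in the battery could carry Aim 2, with a much larger error rate. The plan does not say so; the power text narrows attention to two scores.
- A reader might infer from "Table 2: NIH Toolbox Cognition Battery Tests" that the composite is undefined because the table does not list it. The table's column is headed for test names as well as tasks, but only the tasks are legible in the available text, so its silence carries no weight.

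**Conclusion.** The point holds as an improvement in efficiency, not as an error. Aim 2 rests on an unadjusted comparison of change although the baseline score is collected and could be a covariate. Under equal variances and r of 0.5 to 0.9, adjustment lowers the variance of the treatment estimate by 25% to 5%. The direction does not depend on those assumptions; the size does.

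The supporting point is that the SAP leaves open which of two powered scores answers Aim 2. Its consequence is modest: at worst an error rate somewhat above nominal for a secondary claim, if either score were allowed to carry it. The choice of cognitive score and method has no bearing on the error rate of the primary BA-FMD test.

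**What to change.** 1. In the Aim 2 analysis, replace the t-test of change by ANCOVA of the month-12 score, with treatment group and the baseline value of the same score as terms. Keep the t-test of change as a sensitivity analysis if wished. The same wording suits BA-FMD and aPWV in Aim 1a; the gain there is not sized here, because the documents give no baseline correlation for them.
2. Name one of the two powered scores, for example the fluid composite, as the deciding Aim 2 score at two-sided 0.05. If the composite is chosen, list its component tests. Report the other scores as supportive estimates with 95% confidence intervals.
3. Fix both choices before treatment-group results are seen.

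The cost is SAP wording only. No visits, data or participants are added, and no complete case is lost, since a change score needs the same two measurements. ANCOVA uses one degree of freedom and assumes a roughly linear relation with baseline. The one real restriction is that an isolated result on a non-deciding score can no longer carry the Aim 2 conclusion.

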- **Experimental Design:** 88 subjects, recruited at the University of Iowa Hospitals and Clinics (UIHC) and The Iowa City VA Medical Center, will be randomized to receive either placebo or curcumin (2000 mg/ day) for 12 months and stratified randomization will be employed based on age \geq 55 yeas ⁸⁻¹⁰ and baseline DM status ¹¹. Block randomization is an alternative for consideration. Study outcomes will be evaluated at baseline, 6 months, and 12 months (except cognitive function will be evaluated at baseline and 12 months only).

- **Curcumin supplementation:** Based on our preliminary data we will use a solid lipid curcumin particle (SLCP, Longvida, Verdure Sciences) at a dose of 2000 mg/d. Based on our preliminary data, we believe this will be an effective dose to improve vascular function in patients with CKD. Longvida will provide the supplement in addition to identical-looking placebo. The randomization table will be generated by [name] and provided to Longvida. Once a subject is randomized, Longvida will package and ship the study drug (curcumin or placebo). The package will only state "study drug" in order to guarantee blinding of all the study staff and participants. As we show in the **Preliminary Data** and **Protection of Human Subjects** sections, curcumin was well-tolerated with a small number of adverse events (mainly gastrointestinal discomfort).

- **Rational for the duration of the study:** In specific aim 2, we intend to evaluate whether curcumin improves cognitive function in patients with CKD. Although our preliminary data suggests that curcumin may improve cognition in as little as 12 weeks, we believe a longer duration is necessary to minimize practice effects from repeated cognitive testing ^{12,13}. Thus, the study duration will be 12 months. In addition, this longer duration will

enhance our ability to detect a benefit on vascular stiffness (specific aim 1). Large elastic artery stiffness reflects structural changes of the extracellular matrix in the vessel wall ¹⁴. Based on this, the longer duration of study will allow the treatment to reverse these structural changes in the vasculature. The vascular measurements will be conducted at baseline, 6 months, and 12 months. In order to reduce practice effects, cognitive function will be measured at baseline and 12 months only.

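### The governing BA-FMD analysis is a complete-case t-test that leaves out month-6 values, and its low-loss rationale sits badly with the SAP's 18% loss allowance

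*SAP*

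**What the plan says.** The SAP's Statistical analysis section compares the 12-month change in BA-FMD between arms with a two-sample t-test and places all outcome analyses under intention to treat. Under Loss to follow-up and missing data it then says: "We thus plan to derive conclusions based on complete case analysis by using two-sample t-test of the outcome variables". The reason given is that little loss is expected. The fallback is: "In the unlikely event of >10% missing data, we will perform multiple imputation under assumption of missing at random (MAR) mechanism", to see whether conclusions change. Those lost and those who complete are also to be compared on baseline characteristics.

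The power section says: "We are going to enroll a total of 88 patients assuming approximately 18% potential loss to follow-up". It assumes that the mean and SD of the change "are 0.70 and 0.90 under curcumin and 0.10 and 0.40 under placebo".

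The Protocol's Experimental Design says: "Study outcomes will be evaluated at baseline, 6 months, and 12 months", with cognition excepted from month 6. The SAP uses the month-6 vascular values in an additional repeated-measures analysis "to compare the two groups in the change in both BA-FMD and aPWV from baseline to month 6 and 12", for which "the compound symmetry covariance structure will be specified".

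**The concern.** The choice of complete cases is argued from low loss, while the same document budgets for a loss well above its own 10% trigger. The 18% is an allowance and not a forecast, so the larger weakness is the governing analysis itself. It excludes randomised participants despite the intention-to-treat statement, and it discards a month-6 measurement of the same outcome for anyone lost after that visit.

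If participants with a poorer month-6 response are more likely to leave, those who remain look better than the full arm. The shift scales with the arm's SD. With SDs of 0.90 and 0.40 it is larger in the curcumin arm at equal loss, so the difference is overstated. It is overstated further if curcumin loses more, and the shifts can largely cancel if placebo loses more.

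The fallbacks cover only part of this. The SAP does not describe the imputation model, say whether it uses month 6, or say which result prevails if the two disagree. Compound symmetry, as specified, has one variance for both arms and both visits, which conflicts with the SAP's own SDs.

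**Working it through.** **The plan's own figure.** With means 0.70 and 0.10, SDs 0.90 and 0.40, two-sided alpha 0.05 and an unequal-variance t-test, power is 94.8% at 36 per arm and 95.3% at 37. The SAP's 37 per group reproduces. At 18% loss, 44 × 0.82 = 36.08 per arm remain, so power is hardly affected. The issue is bias.

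**How likely is the trigger?** The SAP gives no denominator, so take all 88 randomised. More than 10% missing then means at least 9 participants (9/88 = 10.2%; 8/88 = 9.1%). Exact binomial P(X ≥ 9):

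| True loss | Probability |
|---|---|
| 18% | 0.985 |
| 10% | 0.523 |
| 5% | 0.032 |

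**Size of the complete-case shift.** Assumptions not in the documents: correlation r between month-6 and month-12 change of 0.3, 0.6 or 0.8; all loss after month 6; dropout probability expit(a − b·z6), where z6 is the standardised month-6 change, b = 0, 0.5 or 1, and a is set to give the stated loss. Then

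E(complete-case difference) = 0.60 + r × (0.90·kC − 0.40·kP),

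where kC and kP are the means of z6 among those retained in each arm, found by numerical integration. For b = 1, k = 0.157 at 18% loss, 0.205 at 24% and 0.108 at 12%. With r = 0.6:

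- 18/18%: 0.60 + 0.6 × (0.90 − 0.40) × 0.157 = 0.647
- 24/12%: 0.60 + 0.6 × (0.90 × 0.205 − 0.40 × 0.108) = 0.685

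All cases, for r = 0.3, 0.6, 0.8 (b = 0 gives 0.600 throughout):

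| Loss, curcumin/placebo | b = 0.5 | b = 1 |
|---|---|---|
| 5/5% | 0.604, 0.607, 0.610 | 0.607, 0.614, 0.619 |
| 10/10% | 0.607, 0.615, 0.620 | 0.614, 0.627, 0.636 |
| 18/18% | 0.613, 0.626, 0.635 | 0.624, 0.647, 0.663 |
| 24/12% | 0.624, 0.648, 0.664 | 0.642, 0.685, 0.713 |
| 12/24% | 0.602, 0.604, 0.605 | 0.604, 0.609, 0.612 |
| 9/27% | 0.596, 0.593, 0.590 | 0.595, 0.589, 0.586 |

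**Precision under random 18% loss.** The complete-case SE is √(0.97/36.08) = 0.164, where 0.97 = 0.90² + 0.40². Using month 6, SE = √{0.97 × [(1 − r²)/36.08 + r²/44]} = 0.163, 0.159 and 0.154 for r = 0.3, 0.6 and 0.8. The gain is small.

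**False-positive rate.** Simulation with 44 per arm, r = 0.6, nominal 5% Welch test, b = 0, 0.5, 1:

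| Loss | Complete case |
|---|---|
| 18/18% | 5.0, 5.1, 6.0% |
| 24/12% | 4.9, 6.0, 7.9% |
| 12/24% | 5.3, 4.9, 5.0% |

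A likelihood analysis using month 6, with unstructured covariance by arm and no baseline adjustment, gave 4.7 to 4.8% in all nine settings.

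**Compound symmetry as planned.** At 18/18%, r = 0.6 and random loss, its null rejection depends on the ratio of month-6 to month-12 SD: 11.5% at 0.6, 7.8% at 0.8, 4.8% at 1.0 and 2.5% at 1.25. Unstructured covariance by arm stayed at 4.6 to 5.0%.

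**Early loss.** If half the loss comes before month 6 and depends on the unseen response (r = 0.6, b = 0.5 and 1):

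| Loss | Complete case | Likelihood with month 6 |
|---|---|---|
| 18/18% | 0.625, 0.647 | 0.611, 0.622 |
| 24/12% | 0.647, 0.686 | 0.619, 0.636 |

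**The case against.** The plan has safeguards that act where the bias is largest. Imputation is almost certain to be triggered at 18% loss, and at 5% loss, where it usually is not, the difference moves to at most 0.62. Month-6 data are used in a planned model; with equal SDs at the two visits, that compound-symmetry model was essentially unbiased in a separate simulation, so the dispute is partly about which analysis is labelled primary. Budgeting 18% while hoping for less is ordinary practice. The bias depends on a correlation, a dropout mechanism and a loss pattern that the documents do not give, and the 7.9% needs both the strongest assumed dependence and twice the loss on curcumin. The compound-symmetry figures concern a secondary analysis and assumed SD ratios. Finally, the proposed baseline-adjusted model rejected 5.2 to 6.4% under the null with uncorrected standard errors, and the small-sample correction was not simulated.

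Most of this stands as a limit on size, and it is why the point is not graver. It does not rescue the governing test. Conclusions are still to be drawn from the one planned analysis that leaves month 6 out, and the SAP does not say what happens if imputation disagrees. Using month 6 also has limits: in the early-loss scenarios it removed only 53 to 60% of the bias (for example, 0.047 reduced to 0.022).

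**Conclusion.** The concern holds and should be fixed, with medium confidence. The low-loss rationale and the word unlikely do not fit an 18% allowance: at that loss the trigger is met with 98% probability, against 52% at 10% loss and 3% at 5%. The governing test is open to bias if loss depends on month-6 response. Under the stated assumptions, the expected difference runs from 0.59 to 0.71 against a true 0.60, always within one standard error, and null rejection runs from about 5% to 7.9%. With random loss there is no bias and only a small loss of precision. The documents do not settle which case applies.

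**What to change.** Before unblinded outcome data are seen:

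- Make the month-12 treatment contrast from the already planned repeated-measures model the governing analysis. Use change at months 6 and 12 as responses, adjust for baseline BA-FMD at each visit, and replace compound symmetry with unstructured covariance separate by arm. Fit by REML with a Kenward-Roger correction, including all randomised participants with any post-baseline BA-FMD.
- Keep the completers' t-test as a sensitivity analysis.
- Run multiple imputation by arm whatever the percentage missing, with month 6 in the model for BA-FMD. Include cognition, although without a month-6 value the gain there will be limited.
- Reconcile the wording on expected loss with the 18% and state which result prevails if analyses differ. A delta-adjusted analysis is optional.

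In a check of the proposed model (1,500 trials per scenario, 18/18% loss, assumed baseline–change correlation −0.3 or −0.5, b = 0 or 1), the mean estimate was 0.598 to 0.608 against 0.60, and the empirical SD was 0.141 to 0.158 against 0.159 to 0.168 for complete case. Part of that gain may come from baseline adjustment. Null rejection of 5.2 to 6.4% without correction is the reason for asking for Kenward-Roger.

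The cost is SAP wording and programming, with no new data or patients. The primary result becomes model-based, differs from the test used for sizing, and still rests on missing at random. The documents do not give the trial's stage. If unblinded outcomes have already been seen, keep the t-test as primary and report the model as a sensitivity analysis.
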